**Table 2. PAAS Curriculum: Program-Targeted Behaviors**

Session	Parent Component	Parent-targeted Behavior	Youth Component	Youth-targeted Behavior	Family Component	Family-targeted Behavior
1	Supportive parenting	Importance of supportive parenting; normative dev. patterns of adolescence; parental expectations and goals; effective ways to support youth goals, dreams	Future orientation	Identify and visualize goals and dreams	Positive parent-child relationship	Build nurturing, supportive relationships; enhance parental involvement
2	Family rules and routines; nurturing, involved parenting	Understand the values of having specific house rules; appropriate and effective punishment for misbehavior	Self-discovery and autonomy	Identify positive self-qualities and capacities; clarification of values and social norms; association between responsibility and autonomy and privilege-granting by parents	Family values	Share family rules and chores; discuss family values; create a family shield of values
3	Adaptive racial socialization; encouraging racial pride	Identifying and managing racial discrimination; preparation for racial bias and promoting racial pride	Dealing with unfair situations	Identifying and clarifying reasons for differential treatment; active coping strategies to manage unfair & difficult situations	Encouraging racial pride	Learn strategies of handling difficult situations; identify special strengths of African-American families
4	Linking school and academic performance to goals and dreams to youths' future orientation	Understand the importance of success in school; learn ways to help youth succeed in school; learn effective ways to be an advocate for your child in school settings	Being cool and smart	Understanding the differences between passive, aggressive and assertive behaviors; adaptive responses that are smart and cool	Positive, affectionate family relations	Identify each other's stressors; reinforce ways to help each other to reach family goals and relieve stress
5	Protecting against dangerous behavior	Understand risk prevalence, overall and for your community; Importance of being an approachable parent	Peer pressure; parents' concerns about peer affiliation	Identify peer pressure; compare risk engagers from non-risk engagers; dealing with temptation; prosocial peer affiliation	Caregivers and youth working together to protect youth from risk behaviors	Develop family plan for handling peer pressure and temptation; share expectations and values about risk and friendship
6	Parental protections that reduce high risk behaviors	Learn how to effectively monitor youth; understand the prevalence of sexual activity in teens; establish expectations about sex	Dealing with sexual and substance use temptations	Identifying and avoiding dangerous situations; connecting temptations, dreams, goals, school and future orientation	Our family plan and pledge for positive youth development	Share expectations, dreams, and hopes; discuss/identify family strengths; establish a family creed of strength, growth and competence

**IIIC.5. Primary Outcome Criteria:** Primary outcome variables include fronto-striatal functional connectivity at rest and while performing the WOF task and youth psychological protective factors (cognitive and emotional self-regulation). Other neural measures/circuits, psychological/social-contextual and behavioral variables (**Appendix 1**) will be used either as supplementary measures or as potential covariates. By sharpening our focus to *a priori* specified neural circuits and psychological measures, we hope to increase statistical power and, in turn, our ability to identify important differences in the responses of these circuits according to youth protective factors.

**IIIC.6. Sample Attrition:** The team has experience with intensive longitudinal studies involving difficult-to-reach samples with retention rates exceeding 90% for short-term follow-up (**IIIC.10a**). Even with a liberal estimate of 20% attrition, we will have 102 participants, which will give us sufficient power to detect medium effects (**IIIC.7e**).

### IIIC.7. Statistical Methods

**IIIC.7a. Data Management:** Data management will be done via remote electronic data capture (*REDCap*). REDCAP was developed at VUMC to insure data integrity and completeness, including compliance with HIPAA (over 300,000 users). Data will be entered immediately after testing on data entry screens designed to duplicate the data collection forms (ACASI; **IIIC.4f.4**). Reports can be generated to track all contacts with the participants.

**IIIC.7b. Procedures for Handling Missing Data:** Missing data will be accounted for by including "missingness" as a covariate if the proportion of missing data is small, or alternatively using multiple imputation methods if the proportion of missing data is large, e.g. >5%.

**IIIC.7c. Data Reduction:** Each hypothesis will be examined using a primary variable, with supplemental information gained from analysis of other related measures (**see IIIC.5**).

**IIIC.7d. Data Analysis:** Descriptive statistics (e.g. means and standard deviations, frequencies and histograms) will be computed for all variables, along with 95% bootstrap confidence intervals. Significance tests will be two-tailed, with  $p < 0.05$ , controlling for multiple comparisons. Pubertal stage/gonadal hormones, gender and SES will be included as concomitant variables in analyses where they are known to correlate with the outcome. These covariates, while not of primary interest, will reduce residual variance and increase the precision of effect estimates for improved statistical power. Secondary analyses will determine if these covariates significantly affect the outcomes. Behavioral/emotional problem score (CBCL/YSR), lifetime history of substance use and dose of the intervention (number of completed sessions) will serve as additional potential covariates.

**IIIC.7d.1. Hypothesis 1:** PAAS will induce greater functional connectivity changes in the reward-drive and cognitive-control (fronto-striatal) circuitry compared to the wait-list condition. Post-treatment neural connectivity

scores will be regressed on group assignment (PAAS vs. wait-list) as the independent variable and baseline (pre-treatment) neural connectivity score as a covariate. Two separate models will be run for resting-state and task-based fMRI connectivity measures. Other covariates (IIIC.7d) will be included if there are group differences.

**IIIC.7d.2. Hypothesis 2: PAAS-induced changes in youth self-regulation (cognitive and emotional regulation) at 3 months will be mediated by PAAS' effects on changes in neural circuitry.** A mediation process will be modeled using a sequential process of the associations between specified brain responses and self-regulation. The Wager/Lindquist Mediation Toolbox (IIIC.4f.2b.6) will be deployed. Mediation effects are estimated from the product of the regression coefficient (a) when a mediator of interest (e.g. neural response) is regressed on the intervention and regression coefficient (b) when the outcome criterion (self-regulation at 3 mon.) is regressed on the mediator, controlling for the intervention effect. The standard error of the mediated effect can be calculated in various ways, including the bootstrap method. This method is referred to as the product-of-coefficients approach for testing mediation, and provides an efficient overall test of mediation processes.

**IIIC.7d.3. Exploratory Analyses:** We will examine whether baseline characteristics moderate PAAS' effect (e.g. if reward-drive [BAS] score/ neural connectivity in the fronto-striatal circuit interacts with PAAS) on improvement in self-regulation. We will assess the association of neural changes (local/whole brain) with behavioral and social-contextual variables targeted by PAAS (i.e. risky behaviors and parenting behavior). Other functional connectivity changes (e.g. default-mode, cognitive and salience networks, and the fronto-limbic circuit) will be identified and the association between functional connectivity patterns at rest and during task performance will be evaluated.

**IIIC.7e. Power Analysis:** Statistical power was estimated with G power 3.1.9.2 software. We used traditional criteria (alpha = .05 two-tailed, power = 80%) to estimate statistical power. [Rather than base power estimates on modest pilot samples, we assessed power by *minimum detectable effect size (MDES)*.] For fMRI studies, Thirion et al. recommend sample sizes of 40 per group for reliable estimates of group differences. Given the multiple variables of interest, we selected larger sample sizes. Randomized subjects will be compared in two conditions using a multiple regression model. With N = 102 participants (after accounting for attrition), a multiple regression would have adequate power to detect an effect size as low as  $r = .31$  ( $R^2 = .10$ ). Cohen considers  $r \sim .10/.30/.50$  to be small/medium/large effect sizes. Power will be sufficient to detect medium effects. Because we will use a repeated measures model with covariates, actual power should be somewhat better. A sample size of  $n = 102$  is also sufficient to detect mediation in an analysis with medium-sized  $\alpha$  and  $\beta$  paths.

**IIIC.8. Timeline:** Table 3 shows the expected timeline of activities for the proposed research.

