### III. RESEARCH STRATEGY

#### III A. SIGNIFICANCE

**IIIA.1. Individual Differences in Adolescent Risk-taking Behavior:** Despite evidence of an overall increase in risky behaviors in adolescence compared to childhood, it is important to recognize the substantial individual differences. Evidence from longitudinal studies suggests that a significant amount of the problematic behavior observed in adolescents is clustered in a small proportion of youth. It is likely that underlying differences in brain function play a role in the dramatic differences in decision-making in these two sub-groups. Thus, we need a better understanding of how individual differences in brain function that underlie the more problematic risk-taking behaviors can be used to address numerous ethnic/racial disparities that continue to plague our society.

**IIIA.2. Neural Substrates of Risk-taking Behavior during Adolescence:** Some developmental neuroscientists postulate that risky behavior during adolescence is the product of the interaction between changes in two distinct neurobiological systems: a reward system, localized in the limbic and paralimbic areas of the brain including the amygdala, ventral striatum, medial prefrontal cortex (mPFC) and orbitofrontal cortex (OFC); and a cognitive-control system, consisting mainly of lateral prefrontal and parietal cortices (including dorsolateral prefrontal cortex [DLPFC]) and their connections to the anterior cingulate cortex (ACC). According to this model, there is a dramatic increase in dopaminergic activity within the reward system around puberty, which increases reward-seeking behavior. This increase in reward-seeking precedes the maturation of the cognitive-control system. Connections between cognitive-control and reward systems gradually unfold during adolescence and lead to better self-regulation and impulse control. The temporal disassociation between the maturation of reward and cognitive-control systems creates a period of heightened vulnerability to risky behaviors.

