### III C. APPROACH

**IIIC.1 Overview:** The conceptual model guiding our study is presented in **Fig 1**. Aim 1 will assess the effects of PAAS on the magnitude of Phase 2 functional connectivity between reward-drive and cognitive-control neural circuitry at rest and during a decision-making task after controlling for pre-intervention (Phase 1) levels. Aim 2 will evaluate if Phase 2 post-treatment neural circuitry changes mediate PAAS' effects on psychological processes (i.e. cognitive and emotional self-regulation) at the 3-month follow-up (Phase 3) after controlling for Phase 1 values. Our overarching hypothesis is that the functional connectivity between reward and cognitive-control networks correlates with self-regulation, and that PAAS increases the magnitude of functional connectivity between these neural networks. In addition to these hypotheses, we will identify characteristics (demographic, neurobiological, psychological, behavioral and social-contextual factors) that moderate PAAS' effects on the relationship between functional brain changes and cognitive-emotional self-regulation in exploratory analyses (IIIC.3b; **Fig 2**).

A total of 128 AA volunteers (ages 11-13 years, 50% male and female) and 128 parents (primary caretakers) will be recruited. Youth and parents will complete assessments on intervention targets (i.e. parenting processes, youth psychological protective factors and cognitions/behaviors associated with HIV and SUD vulnerability). fMRI scans will be acquired in the youth to assess functional connectivity between reward-drive and cognitive-control neural circuitry during rest and while performing a decision-making task involving probabilistic monetary rewards. A second task that assesses general impulsivity/motor response inhibition (in contrast to reward-drive) will be included as a supplementary measure. Following assessments, the families will be randomized to either PAAS or a wait-list control condition for 6 weeks. fMRI scans will be repeated after 6 weeks to measure functional brain changes from pre-to-post intervention. They will repeat the intervention-targeted assessments 3 months later, after which the wait-list controls will be offered PAAS as a benefit for participation in the study (IIIC.4f.1; **Fig 6**).

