**IIIC.4b. Inclusion Criteria:** Participants will be between 11 years 0 months and 13 years 11 months of age and of AA racial status (self-reported). They will speak and read English. The youth and a parent/legal guardian must agree to participate in the 6-week PAAS program and complete the assessments.

[figure not shown]
**IIIC.4c. Exclusion Criteria:** Youth with major medical problems (e.g. neurological disorders) or on medications that affect the central nervous system will be excluded. Persons with behavioral/emotional problems at a clinical level (by parent and/or youth report) will be excluded because psychiatric disorders can affect neural responses. Pregnant females, or those of suspected of being pregnant, will be excluded. Individuals with color-blindness, claustrophobia or metallic implants will be excluded. Persons using alcohol and/or drugs in the three days prior to neuroimaging studies (based on history and/or urine drug screen) will be excluded.

**IIIC.4d. Rationale for the Restricted Age Range:** We selected 11-13 year-olds because most youth at this developmental stage do not abuse alcohol or drugs and are not sexually active, but they are typically beginning to experience social pressures and pubertal changes that increase their vulnerability to these behaviors; in our previous samples of AAs, about 20% had ever used alcohol/drugs and 10% had sexual debut. Second, we have found the PAAS intervention to be more salient for youth at this age (IIIC.3b). Third, sensation-seeking traits and the brain regions that respond to rewards (specifically the striatum) are more active around this period, with heightened vulnerability to risky behaviors in the context of an immature cognitive-control system.

**IIIC.4e. Rationale for Excluding Other Ethnic/Racial Groups:** AA youth are selected because of the high rates of risky behaviors and associated negative consequences (e.g. HIV/AIDS, violence) compared to other groups (see II). PAAS was designed specifically for AAs. Although it contains elements that are generalizable, some components of the program are specific to AA (e.g. adaptive racial socialization, and managing stress associated with racial discrimination). If neurobiological mediators of this program are identified, future investigations will be able to test these effects in other ethnic/racial groups, by modifying ethnic-specific elements of the intervention.

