**IIIC.4f.3h. Physical/Laboratory Measures:** Participants will rate their pubertal status based on the illustrations of stages of pubertal development. Blood will be drawn for serum gonadal steroids (estradiol, progesterone and testosterone). In exploratory analyses, we will examine the effect of pubertal stage and gonadal hormones on neural responses, as there likely will be a greater variation in pubertal maturation at this age range (11-13 years). A urine test will provide qualitative and quantitative information on substance use (amphetamines, benzodiazepines, cannabinoids, cocaine, ethanol, opiates, oxycodone, and phencyclidine). Sexually active females will have a urine test to rule out pregnancy for the MRI studies.

**IIIC.4f.4. Data Collection Protocol:** Trained staff members will conduct the assessments. They will have a minimum of 40 hours of training and supervised practice on how to obtain informed assent/consent, build rapport, interview, and assist participants on the computer-based data collection system and PAAS-technology program. Data collection will occur at clinical sites, the PI's lab, participants' homes or community settings, based on the participants' choices. Families will use the computer-based data system to complete assessments using audio computer-assisted self-interview (ACASI) procedures, which are integrated into the remote data management system (IIIC.7a). Each computer will have headphones, the computer screen will display one question at a time, and all information that appears on-screen also will be read to participants by the computer. Compared with face-to-face interviews and self-administered surveys, ACASI offers privacy and confidentiality that, in turn, elicits less social desirability bias, and more accurate reports on questions about sensitive issues or negative behaviors. The use of ACASI in our previous studies reduced missing data, increased consistency and eliminated literacy requirements. Psychiatric diagnostic interviews will be conducted by trained research assistants. [name] was involved in the development and testing of the K-SADS-PL. Prior to initiating the study, reliability will be assessed (requiring  $\geq 85\%$  agreement). In order to avoid reliability drift over time, reliability checks will be made annually. All interviews will be audio-taped, and a random selection of 15% of the interviews will be co-rated by [name].

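### Age is in neither the covariate list nor the Hypothesis 2 mediation equations, which leaves the observational connectivity-to-self-regulation path open to a plausible confounder

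*Combined protocol and SAP*

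**What the plan says.** - **Covariates (IIIC.7d).** "Pubertal stage/gonadal hormones, gender and SES will be included as concomitant variables in analyses where they are known to correlate with the outcome". A second sentence adds the CBCL/YSR score and says that "lifetime history of substance use and dose of the intervention (number of completed sessions) will serve as additional potential covariates". Age is in neither sentence.
- **Entry rule for Hypothesis 1 (IIIC.7d.1).** Baseline connectivity is always in the model. Beyond that, "Other covariates (IIIC.7d) will be included if there are group differences".
- **Hypothesis 2 (IIIC.7d.2).** The mediated effect is the product of path a (mediator on intervention) and path b. Path b is the coefficient "when the outcome criterion (self-regulation at 3 mon.) is regressed on the mediator, controlling for the intervention effect". No other control is named.
- **Aim 2 in the overview (IIIC.1).** Self-regulation is assessed "at the 3-month follow-up (Phase 3) after controlling for Phase 1 values". IIIC.7d.2 does not repeat this.
- **Age range (IIIC.4b).** "Participants will be between 11 years 0 months and 13 years 11 months of age".
- **Randomisation (IIIC.4f.5).** The strata are gender and Tanner stage (I–II, III–V). Age is not a stratum.
- **Developmental theory (IIIA.2).** "Connections between cognitive-control and reward systems gradually unfold during adolescence and lead to better self-regulation and impulse control".
- **Potential confounds (IIIC.10b).** Age-range confounds are said to be dealt with, by reference to IIIC.4d. That section justifies the restricted range; it does not adjust for variation within it.

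**The concern.** Path a is protected by randomisation. Path b is an observational association between week-6 connectivity and 3-month self-regulation. Anything that raises both, other than through the measured connectivity, can look like neural mediation. In a sample running from just 11 to nearly 14, age is an obvious candidate. It could act on self-regulation through schooling, peers or brain regions outside the fronto-striatal mediator.

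The existing safeguards cover this only in part. Pubertal stage and hormones capture some of the maturation, but they enter only where a correlation with the outcome is known. The group-difference rule given for Hypothesis 1 would not help if carried over to Hypothesis 2, because a variable perfectly balanced between arms can still confound path b. At stake is the central mechanistic claim of Aim 2.

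**Working it through.** **1. The plan's own figures.** Analysed N: 128 × 0.80 = 102.4, so 102, as in IIIC.6. IIIC.7e gives a minimum detectable r = .31 (R² = .10) at 80% power, two-tailed alpha .05. Using the noncentral F with λ = N·f² and f² = R²/(1 − R²), an omnibus test with three predictors gives R² = .1001 (r = .316), and power .7995 at R² = .10. The figure is reproduced; the number of predictors is not stated, and three is inferred.

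**2. Spurious path b for the equation in IIIC.7d.2.** Let true b = 0. Treatment is randomised and so unrelated to age. The standardised spurious b is then corr(age, mediator) × corr(age, outcome). The documents give neither correlation, so a range is assumed. The rejection rate is from the noncentral F with 1 and 102 − 3 = 99 df. For example, at .3/.3, b = .09, f² = .0081/.9919 = .0082 and λ = 102 × .0082 = .83.

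False mediation also needs a significant path a. For an assumed path a of r = .30, its power at N = 102 is .882.

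| Age correlations | Spurious b | Path b rejected | × .882 = false mediation |
|---|---|---|---|
| .1/.1 | .01 | .051 | .045 |
| .2/.2 | .04 | .069 | .061 |
| .3/.3 | .09 | .148 | .131 |
| .4/.4 | .16 | .368 | .325 |

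A joint-significance simulation (6,000 replicates) gave 5.7%, 13.5% and 31.8% at .2, .3 and .4, and 4.5%, 4.9% and 4.6% with age in the model. A separate simulation gave about 6%, 14% and 34% without age. Hence the ranges 13–14% and 32–34%.

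**3. What the other adjustments remove.** A further simulation (3,000 replicates per row) assumed stability .5 for connectivity and self-regulation, an age–Tanner correlation of .6, and Tanner stage dichotomised. It gave these path b rejection rates:

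| Age correlations | Treatment only | + Tanner | + Phase 1 values | + Phase 1 and Tanner | + Phase 1, Tanner and age |
|---|---|---|---|---|---|
| .2/.2 | 6.8% | 6.0% | 5.2% | 4.8% | 4.9% |
| .3/.3 | 14.5% | 9.9% | 5.4% | 5.0% | 5.2% |
| .4/.4 | 35.6% | 23.2% | 8.4% | 6.8% | 4.4% |

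The Monte Carlo standard error near 5% is √(.05 × .95/3000) = .004, so differences of a few tenths of a point are noise. Multiplying the Phase 1 column by .882 gives .052 × .882 = .046, .054 × .882 = .048 and .084 × .882 = .074, that is, about 5%, 5% and 7% false mediation. Controlling Phase 1 connectivity could raise the power of path a, but the joint rate cannot exceed the path b rate in the table.

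**4. Cost in power.** The path b model has 2 predictors as written. Adding age, pubertal stage (one term), Phase 1 connectivity and Phase 1 self-regulation makes 6, leaving 102 − 7 = 95 df. Power for one coefficient at partial r = .31 is .9034 with 2 predictors and .9031 with 6. The minimum detectable partial r stays at .270.

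**The case against.** A reader might infer that the plan's own theory makes age a common cause of connectivity and self-regulation. The text does not support that. The IIIA.2 sentence describes a chain: connections mature and thereby improve self-regulation. A pure chain through the mediator does not confound path b. Confounding needs a separate effect of age on self-regulation, which is plausible but is not stated in the plan. This objection stands, and it limits the point to a plausible confounder.

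The plan also locates the developmental change around puberty, stratifies on Tanner stage, measures gonadal hormones and lists both as covariates. Using pubertal status instead of calendar age within a narrow band is a defensible choice. This stands in part: under the assumptions above, Tanner stage alone lowers the path b rejection rate but leaves 9.9% at .3/.3 and 23.2% at .4/.4, and its entry is conditional.

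The strongest objection is that IIIC.1 promises control for Phase 1 values, which removes most of the bias. A reader who took the 13–34% range as the error rate of the plan as intended would be wrong. Those figures apply only if IIIC.7d.2 is followed without IIIC.1. What remains is that the two sections differ, and the section an analyst would implement is the one without baseline control.

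**Conclusion.** The point holds in a limited form. Age is missing from the covariate list and from both Hypothesis 2 equations, path b is observational, and nothing in the plan guarantees that within-range age differences are adjusted for.

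The size cannot be fixed from the documents. At age correlations of .2 or less the inflation is negligible. At .3 to .4 it is material (13–14% to 32–34% false mediation) under the equation in IIIC.7d.2. It is nil to small (about 5% to 7%) if Phase 1 connectivity and self-regulation are controlled. These figures rest on N = 102, true b = 0, path a r = .30, equal age correlations with mediator and outcome and, for the baseline-adjusted case, stability of .5.

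For Hypothesis 1 there is no bias argument, because the comparison is randomised. Nor do the documents support a claim of a large precision gain there: baseline connectivity is already in the model, so the gain from age is probably small. Severity is low to moderate.

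**What to change.** - In IIIC.7d, name age at Phase 1 and pubertal stage as prespecified covariates that enter regardless of observed correlations or group differences. Use them in both Hypothesis 2 equations and in the Hypothesis 1 models.
- In IIIC.7d.2, write out both equations with Phase 1 connectivity and Phase 1 self-regulation included, so that the section agrees with IIIC.1.

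The cost is a few lines of text and, in the path b model, four degrees of freedom (99 to 95, counting pubertal stage as one term). Power is essentially unchanged and N need not change. No new data are needed: eligibility is set in years and months, so age must already be established, and pubertal stage and the Phase 1 measures are already collected.
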